#### Primary outcome measures

The Strengths and Difficulties Questionnaire (SDQ) (Goodman et al., 1998) is a brief behavioural screening questionnaire used in 2-17-year-olds. It consists of 25 items divided between 5 scales: emotional symptoms (5 items), conduct problems (5 items), hyperactivity/inattention (5 items), peer relationship problems (5 items), and prosocial behaviour (5 items). The first 20 items are added together to generate a total difficulties score. In low-risk or general population samples, an alternative three-subscale version of the SDQ can be used, divided into 'internalising problems' (emotional + peer symptoms, 10 items), 'externalising problems' (conduct + hyperactivity symptoms, 10 items) and the prosocial scale (5 items).

Secondary outcome measures

- The Eating Disorder Diagnostic Scale (EDDS) (Stice et al., 2000) is a 22-item self-report tool designed for individuals aged 13 to 65 that simultaneously assesses diagnostic symptoms of anorexia nervosa, bulimia nervosa, and binge-eating disorder by asking about body image, eating patterns, and compensatory behaviours over the past 3 to 6 months. Items use a combination of Likert, yes-no, frequency, and write-in response formats.
- The Sleep Condition Indicator Questionnaire (SCI) (Espie et al., 2014) is an 8item rating scale measuring sleep problems. The eight items consist of a general
  question on the period of time the individual has had sleep problems. These
  items are rated on a scale from 0 to 4; 4 being the best (e.g., no problem/less
  minutes to fall asleep/very good sleep quality) and 0 being the worst (e.g. >1 year
  sleep problems/more than an hour to fall asleep/very poor sleep quality).
- The Self-Injurious Thoughts and Behaviours Interview (SITBI) (Nock et al., 2007) is a structured interview that assesses the presence, frequency, and characteristics of a wide range of self-injurious thoughts and behaviours, including suicidal ideation, suicide plans, suicide gestures, suicide attempts, and non-suicidal self-injury (NSSI). Only the NSSI section of the interview will be used, modifying the term NSSI to "self-harm" to include all self-harm behaviour regardless of intent.
- The Self-Efficacy Questionnaire for Children (SEQ-C) (Muris, 2001) includes three 8-item scales that measure academic, social, and emotional self-efficacy. The academic self-efficacy scale includes questions about the person's perception of achieving academic goals. The social self-efficacy scale addresses social challenges, and the emotional self-efficacy scale includes questions about coping with unpleasant problems or events.
- The World Health Organisation- Five Well-Being Index (WHO-5) (WHO, 1998) is a short self-reported measure of current mental well-being suitable for children aged 9 and above. The WHO-5 consists of five statements, which respondents rate on a scale from 0 to 5 in relation to the past two weeks (0 = "At no time", 1 = "Some of the time", 2 = "Less than half of the time", 3 = "More than half of the time", 4 = "Most of the time", 5 = "All of the time"). The total raw score, ranging from 0 to 25, is multiplied by 4 to give the final score, with 0 representing the worst imaginable well-being and 100 representing the best imaginable well-being. Item response theory analyses in studies of CYP indicate that the measure has good construct validity as a unidimensional scale measuring well-being in this population (Winther Topp et al., 2015).
- Active trackers: the questionnaire contains 8 compulsory questions (sleep quality, sleep quantity, mood, motivation, anxiety, loneliness, appetite, and exercise) and 11 optional questions (racing thoughts, negative thinking, hopefulness, headaches, irritability, confidence, sociability, energy levels, productivity, self-care, leisure, and a custom metric called "your measure"). Most self-reported questions are on a scale of 1-7 and contain a slider. Sleep quantity and exercise time record the number of hours and minutes completed per day.

- Passive trackers on the app: location, step count, background noise level, ambient light, battery level, app usage on phone (Android only)

Acceptability and usability measures

 Usability/engagement metrics over the study period on the MindCraft app, such as the number of data entries per active tracker, the number of individuals who enabled passive tracking, the number of individuals who enabled each optional active tracker, and the total number of days/weeks the app was accessed.

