#### 3.3 Intervention

#### Frontend design

The MindCraft app is designed with a modular and adaptable framework to facilitate future improvements, support different study questions and provide customisation options to meet individuals' needs and favour engagement (Kadirvelu et al., 2023). The MindCraft app is not classed as a medical device and is not CE-marked. The MindCraft app will be used as a research tool only, and we do not intend to commercialise the app in the future. The key modular components include:

- 1. Customisable active questions: MindCraft allows users to select daily active questions tailored to their unique mental health objectives. Participants are free to select among 8 required and 11 optional trackers.
- 2. Configurable passive data: users can choose which passive data they wish to share, ensuring that they have control over their privacy. The passive trackers include phone and app usage, battery level, location (collected when there is a significant change in the user's location), steps, background noise (collected only when the app is in the foreground) and ambient lighting.

Users can set their active and passive data sharing preferences during the initial onboarding process and can also modify them at any time through the app's settings. MindCraft app is available for free download from the Apple Store and Google Play Store. A valid study ID code is required to use the app (Figure 3). The MindCraft app comprises 3 main tabs in its User Interface: the main tab, the progress tab, and the settings tab (Figure 4)

[figure not shown]

Figure 3. Login screen.

[figure not shown]

Figure 4. Main Tab and Progress Tab.

 Main tab (Figure 4): The app incorporates visual representations of users' mood and mental well-being markers, which have been shown to increase engagement. The main tab is the first view of the app when launched by a registered user. Here, the user can self-report a questionnaire related to their mood and well-being. The questionnaire contains 8 required questions (sleep quality, sleep quantity, mood, motivation, anxiety, loneliness, appetite, and

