exercise), as well as 11 additional questions (racing thoughts, negative thinking, hopefulness, headaches, irritability, confidence, sociability, energy levels, productivity, self-care, leisure, and a custom metric called "your measure"). The user can manage the optional questions through the settings tab. Each question can only be answered once a day; thus, the question will disappear after each submission. Most of the self-reported questions (such as mood and sleep quality) are on a scale of 1-7 and contain a slider. Other questions (such as sleep quantity and exercise time) collect numerical data from text boxes, and the input is type-checked to ensure only valid inputs are stored (e.g., numerical numbers and not text).

 Progress tab (Figure 4): The progress tab charts the self-reported updates given by the user throughout the study. Selecting the data of interest causes the graph view to display the historical data and the average score for the selected period.

[figure not shown]

Figure 5. Settings Tab.

Settings tab (Figure 5): In the settings tab, the user can manage the active and passive data settings, read the privacy policy, and withdraw from the study. The app allows the user to enable or disable the optional active data questions that are most relevant to them. The "Help" option under the Settings tab allows users to seek support when needed. To facilitate this, MindCraft lists four external organisations: Shout, YoungMinds, Best For You NHS, and Kooth - along with a brief description of each organisation and links to their websites.

Personalised digital Al-based recommendations (experimental intervention group) The experimental arm will deliver personalised behavioural recommendations (Al nudges) via the MindCraft mobile app (Figure 6). This reinforcement learning

recommendation system (Figure 1) personalises and dynamically delivers digital Al nudges based on user mental health states (as measured by active and passive trackers) and ratings of the nudges to improve mental health and well-being.

For example, participants self-reporting low mood and/or low step count might be nudged to "take a walk outside". Then, if participants rate this nudge positively, they will be provided with similar recommendations in the future. However, if they rate the nudge negatively because, for example, they do not like walking (and maybe prefer different forms of exercise), they will receive different future nudges, such as "do some light stretching".

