Participants will be followed up at 1 month. If data collection is carried out remotely, baseline and follow-up measures will be collected via an online Qualtrics questionnaire sent to the participant's email. If data collection is carried out in person, participants will complete the baseline (and follow-up) questionnaires through a Qualtrics link (separate from the Consent Form) on their mobile phones.

Completion of the baseline and outcome assessments should take a maximum of 30 minutes. No identifiable information will be collected. Participants will be assigned a unique participant ID, which they will use to complete the baseline and follow-up assessments and sign in to the study app (see Data Management section). Based on their ID, participants will be randomised to different versions of the MindCraft app (see Randomisation).

Reimbursement will be provided upon completion of the study, with the mode of reimbursement determined by each participating school. Schools may choose to distribute vouchers to students or receive the funds centrally to support researchand mental health—related activities, such as travel for workshops at Imperial.

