#### Primary analyses:

- Repeated measures analyses (using a mixed effects linear regression model with a random effect on participant) will be used to compare primary outcomes across follow-up points. Baseline SDQ scores will be included as covariates. The primary endpoint is the intervention difference at 1 month. As multiple analyses are performed to compare both the experimental interventions and the active control with the control, and to compare the experimental intervention with the active control, a multiplicity adjustment will be made with a Bonferroni correction. We will also carry out sub-analyses of primary outcomes based on participants' demographic characteristics/adding them as covariates in the MLM.

Secondary analyses:

- The same modelling approach as primary analyses will be used for secondary outcomes where possible.
- A Complier Average Causal Effect (CACE) analysis will be used to provide an estimate of intervention effect, accounting for pre-specified per-protocol adherence and compliance with the intervention while retaining the benefits of randomisation. Such models will be performed for the primary and secondary outcomes at 1-month follow-up using observed data only and will include the covariates adjusted for in the regression models.
- The pattern of missing outcomes will be examined, and multiple imputations will be used to impute primary and secondary continuous outcomes. Imputation models will be informed by treatment arm, baseline scores, other covariates to be included in the model, and other baseline characteristics found to predict outcome or propensity for missingness (logistic regression models will be used to investigate the associations between baseline characteristics and missingness). Results of imputed models will be compared to the primary analysis complete case ITT models. We will carry out sensitivity analyses to estimate the intervention effect, including all missing data.
- We will estimate the causal effect of the intervention using two-stage least squares (2SLS) regression to account for potential endogeneity in nudge exposure. Random assignment to treatment group (T1 or C2 vs. control) will be used as an instrument for actual exposure. The first stage will model nudge exposure as a function of assignment; the second stage will regress the outcome on predicted exposure. This approach will yield a local average treatment effect (LATE) among compliers. Robust standard errors will be used throughout.

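### Section 3.7 makes user-switchable trackers and sensors secondary outcomes, so between-arm comparisons on them would rest on subsets that pupils select after allocation; Sections 2 and 3.6 do not list them as outcomes

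*Protocol*

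**What the plan says.** **What counts as a secondary outcome.** In Section 3.7 the secondary outcome list runs on past the questionnaires to two app-based entries. One is the active trackers: 8 compulsory questions and "11 optional questions (racing thoughts, negative thinking, hopefulness" and so on, ending with a custom item that the user defines. The other is "Passive trackers on the app: location, step count, background noise level, ambient light, battery level, app usage on phone (Android only"). Acceptability and usability measures follow under a separate label, so the trackers are presented as outcomes and not as engagement data. The secondary objective in Section 2 and the assessment list in Section 3.6 name only the EDDS, SCI, SITBI, SEQ-C and WHO-5.

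**Who decides what is recorded.** Section 3.3 says of the optional questions: "The app allows the user to enable or disable the optional active data questions that are most relevant to them". For sensors, "users can choose which passive data they wish to share". On timing: "Users can set their active and passive data sharing preferences during the initial onboarding process and can also modify them at any time". One sensor also depends on use of the app: "background noise (collected only when the app is in the foreground").

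**When allocation takes effect.** Section 3.5 says: "Based on their ID, participants will be randomised to different versions of the MindCraft app". The same ID is used to sign in.

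**How secondary outcomes are analysed.** Section 3.9 says: "The same modelling approach as primary analyses will be used for secondary outcomes where possible". It also plans multiple imputation of continuous secondary outcomes, informed by arm, baseline scores and other baseline characteristics.

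**The concern.** Randomisation protects a comparison when outcomes are sought from everyone randomised, whatever happens after allocation. Here, whether a pupil contributes a value for an optional tracker or sensor is the pupil's own choice. It is made after the app version is set and can be revised throughout the four weeks. The stated reason for enabling a question is its relevance to the pupil, so enabling plausibly tracks the symptom being measured.

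The arms also differ in what the trackers do. In the experimental arm they drive the nudges; in the self-monitoring arm they feed only the charts. A pupil who gets nudges may keep, add or drop a tracker for reasons that a self-monitoring pupil does not have. Background noise is sampled only while the app is in the foreground, so an arm that opens the app more is sampled at different moments. The custom item has no common content to compare between pupils.

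At stake is the meaning of any reported arm difference on, say, negative thinking or noise. It could reflect who was recorded, or when, and not an effect of the nudges. The planned imputation does not clearly repair this: the baseline assessment in Section 3.6 contains no tracker values, and switching a tracker on or off may depend on experience after allocation that the listed imputation variables do not capture.

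**Working it through.** **1. The sections side by side**

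| Question | Protocol place | Content |
|---|---|---|
| Are trackers secondary outcomes? | 3.7 | Yes: active (8 compulsory plus optional) and all passive |
| | 2 and 3.6 | Not named; five questionnaires only |
| Who switches them, and when? | 3.3 | The user, at onboarding and at any time after |
| Is the arm already fixed then? | 3.5 | Yes, through the sign-in ID |
| Is there a tracker value before allocation? | 3.6 | None described |
| Planned analysis | 3.9 | Primary model, where possible |
| Are the required trackers mandatory? | 3.7 and 3.3 | 3.7 calls them compulsory; 3.3 also says participants choose freely among required and optional ones |

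Section 3.7 does count how many pupils enabled each optional tracker and passive tracking, but only as a usability metric.

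**2. How large could the bias be?** The protocol gives no figure for tracker uptake or for its link with severity, so there is no plan figure to reproduce. What follows is an illustration on assumed inputs.

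*Model.* There is no true effect. The outcome (severity) has SD 1. A pupil enables the tracker when a latent variable, correlated r with severity, exceeds a cut-off z such that a share p enables. Then

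mean severity among enablers = r × φ(z)/p.

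The spurious arm difference is the difference between these means in the two arms.

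*Values of φ(z)/p:* 1.159 at p = 0.3, 0.966 at p = 0.4, 0.798 at p = 0.5.

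*Results with r = 0.3:*
- p = 0.4 against 0.5: 0.3 × 0.966 − 0.3 × 0.798 = 0.290 − 0.239 = **0.050 SD**.
- p = 0.3 against 0.5: 0.3 × 1.159 − 0.239 = 0.348 − 0.239 = **0.108 SD**.
- Equal p and equal r in both arms: **0**.

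*Equal uptake, different selection.* With p = 0.4 in both arms but r = 0.3 in one and 0.15 in the other: 0.290 − 0.145 = 0.145 SD. This case needs the link with severity to be halved in one arm, and nothing in the protocol indicates that. It shows only that equal uptake is not by itself a safeguard.

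**3. Effect on a test.** Take the 168 completers per arm in Section 3.8. The standard error is √(v₁/(168p₁) + v₀/(168p₀)), where v = 1 − r²λ(λ − z) and λ = φ(z)/p.
- p = 0.4 against 0.5: standard error 0.159, two-sided rejection rate at the 5% level 6.2%.
- p = 0.3 against 0.5: standard error 0.172, rejection rate 9.6%.
- Equal selection: 5.0%.

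At the Bonferroni level for three comparisons (0.05/3 = 0.0167) the first two become 2.2% and 4.0%.

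**4. Other assumptions.** For enabling of 60%, 70% or 80% in one arm against 50% in the other, and |r| from 0.2 to 0.5, the difference runs from 0.03 to 0.22 SD.

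**The case against.** The strongest reply is that the protocol never promises an arm comparison on these data. No objective or hypothesis mentions a tracker, and Section 3.9 limits the shared model to cases where it is possible. A daily stream with no baseline score hardly fits a model that adjusts for baseline and targets one month, and its handling could be left to the SAP. This stands in part: the between-arm test is a consequence of the Section 3.7 classification, not an explicit commitment. But the protocol names no exclusion, and an SAP that follows it would start from a list that includes these trackers.

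Second, choice after allocation is not choice caused by allocation. The two nudge arms are to be blind and their nudges share a format, so onboarding choices may well be alike in those arms. This stands: bias needs selection that differs by arm. Later changes of settings, tracker-driven nudges and a self-monitoring group not listed as blind make that possible; none makes it certain.

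Three stronger readings are tempting, and the documents do not support them:
- A reader might infer that nudges run from first use, so that no entry can precede them. The protocol does not say so, and personalised nudges need some tracker input first. What can be said is that no pre-intervention tracker baseline is specified.
- A reader might count the Android-only restriction on phone app usage as a bias. Phone type is a pupil characteristic that randomisation balances in expectation, so the restriction reduces numbers without favouring an arm.
- A reader might set the illustrative differences against the pilot's d of 0.137 and conclude that they could produce the trial's effect. That d is the effect used to size the trial, not a tracker effect.

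The compulsory trackers also go missing when pupils do not use the app, so restricting outcomes to them reduces selection without removing it.

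**Conclusion.** The concern holds as a fault in outcome classification. Section 3.7 turns measurements that pupils switch on and off after allocation into secondary outcomes, and Sections 2 and 3.6 do not agree with it. Between-arm analysis of the optional trackers and passive sensors would compare self-selected subsets, and it is biased if enabling, disabling or app use responds to the nudges.

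The size is unknown. The 0.05 to 0.11 SD illustration rests on an assumed correlation of 0.3, assumed enabling gaps of 10 to 20 percentage points and a bivariate normal selection model; under identical selection in each arm it is zero. The protocol makes differential selection possible but does not show that it will occur.

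The SDQ primary outcome and the five questionnaire outcomes are unaffected, so the point does not touch the trial's main conclusion. It is worth correcting because the change is cheap and no stated objective depends on these comparisons.

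**What to change.** 1. Reconcile Sections 2, 3.6 and 3.7: move the optional active trackers, including the user-defined item, and all passive sensors to descriptive or engagement measures, and state that no between-arm effect will be claimed on them.
2. If app data are kept as secondary outcomes, restrict them to the 8 compulsory trackers, add them to Sections 2 and 3.6, analyse by randomised arm, and report missing entries by arm, because non-use still causes selection.
3. Correct the Section 3.3 sentence that describes the required trackers as open to choice, so that it agrees with their compulsory status in Section 3.7.

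These are text changes: no new data are collected, and delivery of the intervention does not change. The cost is the loss of exploratory inferential claims on the optional and passive data, which can still be described and used by the app.

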### 3.8 Sample Size

The sample size for the internal pilot was 50 participants per group, defined a priori. A power analysis using the observed effect size from our internal pilot interim analyses (average Cohen's d = 0.137; f = 0.139) suggested that a total of 505 participants (168 per group) would be needed to detect between-group differences with 80% power at  $\alpha$  = .05. After adjusting for an anticipated 40% attrition rate, this increases to 842 participants (281 per group). However, our sub-analysis of high-risk participants showed a substantially larger effect size (average Cohen's d = -0.419; f = 0.462), suggesting that a smaller sample may be sufficient to detect meaningful intervention effects in this group. The sample size is an estimate and may differ from the actual sample size.

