#### Secondary objectives:

- To examine the effectiveness of personalised AI nudges vs non-personalised digital self-help using generic CBT principles vs self-monitoring control on secondary outcomes [Eating Disorder Diagnostic Scale (EDDS); Sleep Condition Indicator Questionnaire (SCI); Self-Injurious Thoughts and Behaviours Interview (SITBI); Self-Efficacy Questionnaire for Children (SEQ-C); World Health Organisation-Five Well-Being Index (WHO-5)] at 1-month follow-up
- To examine the efficacy of personalised AI nudges on improving mental health in CYP in a low-risk group (primary prevention) and reduce poor mental health in a high-risk group (secondary prevention) at 1-month follow-up
- To explore potential mediators and moderators of beneficial effects of Al nudges

**Hypothesis**: Al nudges will be more effective than non-personalised digital self-help using generic CBT principles (active control group) and self-monitoring control at reducing CYP SDQ scores at 1-month follow-up

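### Section 3.8's 80% power fits an overall three-arm test at .05, not the Bonferroni-corrected pairwise comparisons that section 3.9 makes primary

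*Protocol*

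**What the plan says.** Three places in the protocol bear on this.

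- **Section 3.8 (Sample Size)** takes its effect size from the internal pilot ("average Cohen's d = 0.137; f = 0.139"). It concludes that 505 participants, 168 per group, "would be needed to detect between-group differences with 80% power at" α = .05, and raises this to 842 (281 per group) for 40% attrition. It does not name a test, a contrast or a multiplicity adjustment.
- **Section 3.9 (Statistical Analysis, primary analyses)** compares AI nudges with self-monitoring, active control with self-monitoring, and AI nudges with active control. For these it states that "a multiplicity adjustment will be made with a Bonferroni correction". Baseline SDQ is a covariate. No overall test of the three arms is described.
- **Section 2 (Study Objectives)** hypothesises that AI "nudges will be more effective than non-personalised digital self-help using generic CBT principles (active control group) and self-monitoring control" in reducing SDQ scores at 1 month. That is a claim against two comparators.

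**The concern.** A power figure should describe the test that decides the trial. Section 3.8 speaks only of differences between groups at .05. Section 3.9 decides on pairwise contrasts at a stricter level, and the hypothesis is met only if two of those contrasts are won. If the 80% belongs to a different test, the real chance of confirming the hypothesis is lower than a reader of section 3.8 would think.

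AI nudges against active control matters most, because it isolates personalisation, which is the study aim. A null result there could easily reflect low power while the protocol reports 80%.

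**Working it through.** **Inputs.** From section 3.8: f = 0.139, α = .05, power 80%, 505 evaluable (168 per arm), 40% attrition. From section 3.2: 1:1:1 allocation. From section 3.9: three pairwise contrasts with Bonferroni, so .05/3 = .0167 each (two-sided tests assumed). From section 2: the AI arm must beat both comparators.

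**1. Reproducing 505 and 842.** For a three-group F test, the degrees of freedom are 2 and N − 3 and the noncentrality is N·f². At α = .05, f = 0.139 gives N = 502. At N = 505 the power is 80.3%. An unrounded f of 0.1385 gives 506, so 505 is within rounding of f. Attrition: 505 / 0.6 = 842.

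Pairwise calculations do not give 168 per arm:

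| Pairwise effect | n per arm at .05 | n per arm at .05/3 |
|---|---|---|
| d = 2f = 0.278 | 204 | 271 |
| d = 0.137 | 837 | 1,116 |

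**2. From f to pairwise effects.** With unit residual SD, f² is the mean squared deviation of the three arm means from their average. The pattern of means has to be assumed.

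- (a) Only the AI arm differs, by D: f² = 2D²/9, so D = 3f/√2 = 0.295 against each comparator.
- (b) Evenly spaced arms with range D: f² = D²/6, so D = f√6 = 0.340 for AI against self-monitoring and 0.170 for AI against active control.

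Pattern (b) gives the widest gap between any two arms that f = 0.139 allows.

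**3. Power at 168 per arm and .05/3.** Power ≈ Φ(d√(n/2) − 2.394), with √(168/2) = 9.165.

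- d = 0.295: Φ(2.703 − 2.394) = 62%
- d = 0.340: Φ(3.121 − 2.394) = 77% by this approximation, 76% by noncentral t
- d = 0.170: Φ(1.560 − 2.394) = 20%

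Power for winning both AI contrasts comes from simulation, because the two share an arm.

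| Pattern | AI vs self-monitoring | AI vs active control | Both |
|---|---|---|---|
| (a) only AI differs | 62% | 62% | 46% |
| (b) evenly spaced | 76% | 20% | 19% |

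Since 0.340 is the widest possible gap, no contrast exceeds about 76% under any pattern.

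**4. Sample size for 80% on AI against active control at .05/3**, same assumptions: (a) 241 per arm, 3 × 241 = 723 evaluable, 723 / 0.6 = 1,205 recruited; (b) 723 per arm, 2,169 evaluable, 3,615 recruited.

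**5. If f is on the unadjusted scale.** Adjusting for baseline divides the SD by 1/√(1 − r²). The protocol gives no r. With r = 0.6 assumed, the SD is multiplied by 0.8. AI against active control becomes Φ(2.703/0.8 − 2.394) = 84% in (a) and Φ(1.560/0.8 − 2.394) = 33% in (b).

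**6. Alternative multiplicity rules** (simulation, 168 per arm, f on the residual scale). The closed procedure is a global test at .05 and then, only if it is significant, each pairwise test at .05. With exactly three arms it controls the familywise error; simulation gave about 5% under both the global null and a partial null.

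| Rule | (a) each AI contrast | (a) both | (b) AI vs active control |
|---|---|---|---|
| Bonferroni | 62% | 46% | 20% |
| Holm | 65% | 52% | 25% |
| Closed | 72% | 64% | 34% |

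**The case against.** Several points on the other side have force.

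- **The omnibus test and the .05/3 are inferences.** Section 3.8 names no test, f = 0.139 exactly gives 502 rather than 505, and section 3.9 states no divisor, which an SAP might fix. This stands as a caution. If Bonferroni covered only the two AI contrasts (.025 each), power would be about 67% for each in pattern (a), and 81% and 25% in (b). The mismatch remains, because section 3.8 mentions no adjustment and section 3.9 requires one.
- **Baseline adjustment may raise power.** The protocol does not say which scale f is on. If it is unadjusted, some contrasts could pass 80%. But section 3.8 claims no such gain and gives no correlation, and AI against active control stays well below 80% in the evenly spaced case at r = 0.6.
- **Bonferroni is valid.** It controls familywise error and gives simple matching simultaneous confidence intervals, which the closed procedure does not. Choosing it is not an error.
- **The planned test is not invalid.** Nothing here biases the estimate or inflates type I error.

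A reader might also infer that power is 20–62% for every key contrast. The documents do not support that: in the evenly spaced pattern that gives 20%, AI against self-monitoring has 76%. Nor is 20–76% a bound. If the active control works nearly as well as AI (means in the ratio 0, 0.75, 1), AI against active control has about 5%.

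A reader might also quote 13%, the power at d = 0.137. That d does not agree with f = 0.139 as an average absolute pairwise effect (which would be about 0.20 to 0.23), so it is a separate question and adds nothing here.

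**Conclusion.** The point holds as a mismatch between sections 3.8 and 3.9. The 80% fits an overall three-arm test at unadjusted .05, while the primary analysis is a set of Bonferroni-corrected pairwise tests and the hypothesis needs two of them. If f = 0.139 applies to the residual SD of the primary model and the correction is .05/3, every planned contrast falls short of 80%, and power to confirm the hypothesis is 46% (only AI differs) or 19% (evenly spaced).

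The mismatch is firm. The exact percentages are not: they depend on the assumed pattern of means, the scale of f and the Bonferroni divisor, none of which the protocol states. The documents support neither a single corrected power figure nor a claim that Bonferroni is wrong.

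**What to change.** **Needed, section 3.8.** Name the test that the sample size is for. Restate power for each pairwise contrast, and for winning both AI contrasts, at the multiplicity-adjusted level. State the assumed pattern of arm means, whether f is on the unadjusted or the baseline-adjusted scale, and the baseline–follow-up correlation if an adjustment gain is claimed. This costs a few sentences and no data, but the restated power will probably be below 80% for at least AI against active control. The sponsor then has to accept that openly or enlarge the trial; the sizes in the working show the scale.

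**Recommended, section 3.9.** Replace Bonferroni with Holm, which is never less powerful, or with the three-arm closed procedure. The closed procedure would also give the overall test behind the sample size a place in the analysis. It needs one changed sentence and no extra participants. The cost is the loss of simple matching simultaneous confidence intervals, and it does not restore 80% per contrast. If Bonferroni is kept, the change to section 3.8 is still required.
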